2.2.3.1 Summary of Overall Clinical Experience with AAV-Mediated Gene Therapy

Based on early experience with SPK-8016, SPK-8011, as well as other AAV-mediated gene transfer trials for hemophilia A and B, the following preliminary observations can be made:

- AAV-based strategies for hemophilia have resulted in sustained expression of clotting factor at levels sufficient to reduce or eliminate the need for clotting factor infusions after a single IV infusion of the AAV-mediated gene.
- Neutralizing antibodies against FVIII or FIX have not been reported for any participant to date.
- [REDACTED]
- [REDACTED]
- [REDACTED]

Although the early results are promising, additional investigation is needed to determine whether there is a transient immunosuppressive regimen that will reliably control immune responses in all patients and allow long-term expression of the donated gene. Based on prior clinical studies, non-clinical studies summarized here, and input from clinical experts in rheumatology, organ transplantation, viral immunology, and bone marrow transplantation, the 2 prophylactically administered immunomodulatory regimens shown in Figure 1 will be evaluated. [REDACTED]

2.2.4 Summary of Non-clinical and Clinical Experience with [REDACTED]

In order to test whether [REDACTED] a non-good laboratory practice (GLP) study in NHPs (Study# IMM_PC2019_001/Covance 8400655) was performed. One of the aims of the study was to rule out the possibility of [REDACTED] blockade increasing the percent of animals developing anti-transgene antibodies, as observed with other immunosuppressive drugs (Mingozzi, 2007). However, since virtually all NHPs will develop neutralizing antibodies against human FVIII following gene transfer (McIntosh, 2013), this assessment would be precluded if a FVIII cassette were used. To this end, FIX was selected as the transgene of choice, as only approximately one third of NHPs develop antibodies against AAV-derived human FIX. An AAV vector serotype, [REDACTED] was used to express the human coagulation factor IX (hFIX) transgene in the livers of healthy male cynomolgus macaques under the control of a liver-specific promoter. Ten Spark100-seronegative animals were divided into 2 experimental groups (5 per group). One of the groups received [REDACTED] 1 day prior to vector infusion. [REDACTED]

No animals demonstrated hypersensitivity or anaphylactic reactions following administration of either [REDACTED] or [REDACTED]. Animals were bled every week for analysis of safety endpoints and hFIX transgene expression levels, along with monitoring [REDACTED]. The study had a follow up duration of 13 weeks post vector infusion. All animals survived to their scheduled sacrifice. The development of subacute decreases in neutrophil counts following single dose [REDACTED] has been observed in human healthy volunteers; no animals in this study developed neutropenia or thrombocytopenia below baseline. Two of 5 animals developed isolated transient elevations of liver transaminases (<2 x upper limit of normal (ULN)) which resolved without intervention without evidence of hepatic obstructive disease

(hyperbilirubinemia) or hepatic insufficiency. Importantly, clinical and anatomic pathology examination of the liver and a panel of 40 organs and tissues showed no macroscopic or microscopic findings in animals receiving the [REDACTED] vector alone or in combination with [REDACTED]. Hepatic transduction as assessed by vector genome copy number in liver (at sacrifice) and by circulating hFIX antigen levels (weekly throughout the study) was not significantly different in the animals that received [REDACTED] compared to controls.

[REDACTED], and in general innate immunity driven by the AAV capsid (Hösel, 2012; Kuranda, 2018) and DNA payload (Martino, 2011; Rogers, 2017), are key triggers of AAV vector immunogenicity including adaptive humoral and cellular responses. Several observations from this study suggest that animals that received [REDACTED]

[REDACTED]

With regard to cellular immune responses, prior studies performed using human CD8+ and CD4+ T lymphocytes identify TNF α as one of the main cytokine signatures of T cell activation in response to AAV (Kuranda, 2018). Thus, peripheral blood mononuclear cells (PBMC) from control animals and [REDACTED]

[REDACTED]

[REDACTED]

2.2.5 Summary of Non-Clinical and Clinical Experience with [REDACTED]

Pre-clinical studies of hepatic artery administration of AAV8-hAAT-hFIX16 were performed in rhesus macaques; in these studies, vector was given alone or together with a short course of

immunomodulation to assess the potential safety and efficacy of the approach. [REDACTED]

[REDACTED]
The [REDACTED]
[REDACTED] and contained the wild type copy of the hFIX cDNA.

[REDACTED]
[REDACTED]
[REDACTED]
[REDACTED]

The regimen of [REDACTED]
[REDACTED]

[REDACTED] The side effect profile was acceptable and there were no SAEs on this regimen. The side effects of immunomodulatory drugs are well described (Post, 2005; Perry, 2005) and include the risk of hepatitis virus reactivation (Savas, 2007; Melon, 2005; Lalazar, 2007; Francisci, 2006; Calabrese, 2006) and the occurrence of B cell lymphoproliferative disorders (Gross, 1999; Pascual, 2007; Bakker, 2007). [REDACTED]

[REDACTED]
[REDACTED]

[REDACTED]
[REDACTED]
[REDACTED]
[REDACTED]
[REDACTED]
[REDACTED]
[REDACTED]

[REDACTED]
[REDACTED]

2.3 Benefit/Risk Assessment

2.3.1 Risk Assessment

The following are potential risks with the administration of any rAAV gene therapy for hemophilia and they will be monitored in this study. Participants should be advised to notify the Investigator(s) immediately and/or seek immediate emergency care, depending on the severity of the reaction, if any symptoms occur.

2.3.1.1 Allergic Reaction or Anaphylaxis

There has been 1 report of symptoms associated with SPK-8011 (rAAV-FVIII) infusion, occurring following SPK-8011 vector infusion at a dose of 2×10^{12} vg/kg. Nonserious events including vomiting, pyrexia, back pain, and myalgia were reported in 1 participant; events started to resolve within 12 hours (per Investigator), all completely resolved in 1 to 3 days with acetaminophen (High, 2018). Participants should be informed of early symptoms and signs of

hypersensitivity reactions, including hives, generalized urticaria, angioedema, chest tightness, dyspnea, wheezing, faintness, hypotension, tachycardia, and anaphylaxis. If such an event occurs, the participant should be instructed to seek immediate medical care.

2.3.1.2 Inhibitor Development

There is a possibility that participants infused with SPK-8016 will develop inhibitors to FVIII, although inhibitor development has not occurred in any participants who have received AAV2-hFIX, AAV8-hFIX (Nathwani, 2014), AAV8-hFIX19 [REDACTED] or BAX-335 (under National Clinical Trial (NCT) 01687608). In addition, inhibitor development has not been reported in any of the 17 participants in the Sponsor initiated Hemophilia A gene therapy study SPK-8011-101. Moreover, no inhibitor development has been reported in the recent BioMarin Hemophilia A gene therapy trial of an AAV5-BDD-hFVIII (BMN-270) (Rangarajan, 2017; Pasi, 2020). Inhibitor development most often occurs within the first 20 infusions of FVIII replacement therapies. The likelihood of participants in this study developing inhibitors will be minimized by including only individuals who have not made inhibitor antibody to FVIII, despite prior heavy exposure to the FVIII infused protein (i.e., those who have had greater than 150 exposure days to FVIII concentrates). Blood samples will be taken at regular intervals to monitor for inhibitor formation during the study and archives will be maintained for possible future analysis should inhibitor development occur.

2.3.1.3 Elevation of Hepatic Transaminases

None of the 4 enrolled participants in study SPK-8016-101 experienced adverse events of transaminitis related to SPK-8016. Of the 17 participants enrolled in the Sponsor's similar hemophilia A gene therapy trial SPK-8011-101, 5 (29%) reported SPK-8011-related adverse events of increase of ALT/aspartate aminotransferase (AST) with severity ranging from mild to moderate in the higher dose groups (2 in the 1.5×10^{12} vg/kg dose cohort, and 3 in the 2×10^{12} vg/kg dose cohort); 1 of the events in the 2×10^{12} vg/kg dose was reported as a SAE. All of them were resolved with steroid intervention. The cause of a transient and asymptomatic hepatic transaminase elevation (i.e., elevated ALT and/or AST) observed in earlier liver-directed AAV-mediated gene transfer clinical trials has not been established. However, some individuals have developed dose-dependent T cell responses to AAV capsids, in the context of elevation in transaminases, and the presumptive mechanism is a memory CD8⁺ T cell response to peptides derived from the AAV capsid of the vector (Mingozzi, 2007). [REDACTED]

In a recent AAV-based gene therapy Phase 1/2 clinical trial investigating AT132 for X-linked myotubular myopathy (XLMTM, NCT03199469 [ASPIRO]), 3 child participants who were older age and heavier weight, had pre-existing liver disease, and were from the highest tested dose cohort of 3×10^{14} vg/kg AT132 experienced SAEs of hyperbilirubinemia. All 3 SAEs

resulted in fatal outcomes caused by progressive liver dysfunction followed by bacterial infections, sepsis, and GI bleeding. The high AT132 dose of 3×10^{14} vg/kg is the highest tested dose for any AAV-based gene therapy to date. Among the 6 child participants treated at 1×10^{14} vg/kg, including 4 with a previous history of hepatobiliary disease, none have yet developed hepatic SAEs despite being years out from treatment ([High-dose AAV, 2020](#); [Audentes Therapeutics, 2020a](#); [Audentes Therapeutics, 2020b](#)). Note that the patient population (adults in the SPK-8016-101 study versus children in the ASPIRO study) and disease severity (Hemophilia A is a less severe disease than XLMTM) are quite different between Study SPK-8016-101 and the ASPIRO study. Moreover, individuals with medically significant underlying liver disease will be excluded from participating in the SPK-8016-101 study and the starting dose that was tested in the study (5×10^{11} vg/kg) is 3 orders of magnitude lower.

2.3.1.4 Anti-AAV Neutralizing Antibody Development

As is expected after systemic administration of AAV vectors, all 4 participants (100%) in study SPK-8016-101 who were treated with SPK-8016 developed neutralizing antibodies to the AAV capsid. This risk seems to have no immediate impact on the expression of FVIII produced by the current AAV gene therapy, but development of neutralizing antibodies to AAV could potentially preclude the chance of a participant receiving another AAV gene therapy in the future.

2.3.1.5 Bleeding Episodes

The proposed dose levels of SPK-8016 may not be sufficient to raise the vector-derived FVIII:C levels to a therapeutic level for controlling and preventing bleeding episodes when the participants halt their prophylactic (factor or non-factor replacement) treatment after vector administration. Clinical experience suggests most patients can stop routine prophylaxis approximately 2 to 4 weeks after receiving SPK-8016 based on the expression of FVIII from the transgene. Participants will be advised to treat their bleeding events with their usual FVIII products during the follow-up observation period. Although bleeding (the nature of the disease) is not considered an adverse event, participants will record the dates of bleeding events, the type and location of the bleed, and the FVIII product and dosage used to treat the bleeding episode in the infusion log (Section 13).

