Corticosteroid therapy may increase the transgene expression from the SPK-8016 expression cassette, similar to SPK-8011, as observed in both animal models and in our clinical observations using both early prophylactic and the reactive application of corticosteroids. In SPK-8011, this effect appears to occur in a dose-dependent fashion; in clinical observation the effect has appeared somewhat greater with initiation of daily oral corticosteroids in a prophylactic fashion in the early weeks after vector delivery when compared to reactive corticosteroids given at later time points. The Primary Endpoint for efficacy for this study is the FVIII activity at steady state,

which Spark does not interpret while any subject remains on corticosteroid treatment. Instead, expression level of steady-state FVIII:C as an efficacy endpoint is evaluated after daily oral corticosteroids or pulse steroids have been discontinued for at least 2 weeks. Note that if the concomitant use of steroids is to have an effect to artifactually increase the FVIII expression to a level greater than the eventual steady state expression (after discontinuation of steroids), this would not trigger an inappropriate escalation of the SPK-8016 dose (which would be a safety concern) but instead might result in an expansion of the present dose cohort or a delay in the decision to dose escalate until after the observation of steady state while off steroid therapy.

[REDACTED]

In consultation with the DMC, further dose exploration may be considered if effective immunomodulation has been demonstrated in any cohort and/or FVIII expression is less than 80% of normal 12 weeks following gene transfer in at least 2 participants.

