4.1.6 Dosing Period (Days 0, 1)

Assessments and procedures to be performed on Dosing Day (Day 0) are described in [Table 1](#). All participants will administer a prophylactic infusion of 50 IU/kg of their current FVIII concentrate the morning of Day 0. This may be self-administered and recorded in the subject infusion log. Site assistance is permitted for the FVIII infusion. On Day 0, participants in Cohort 2 will receive a dose of [REDACTED] intravenously over 60 minutes, with the [REDACTED] infusion to be completed at least 4 hours (up to 24 hours) prior to the start of vector administration. The [REDACTED] dose will not exceed [REDACTED] (Please see [REDACTED] prescribing information [[Genentech, 2019](#)]). Participants will receive a single IV infusion of SPK-8016 at the vector-administration center. The complete dose of SPK-8016 will be infused via infusion pump over approximately 60 minutes. Vital signs will be taken at various time-points from the start of infusion (see [Table 1](#)).

Blood samples for immune profiling will be collected pre-administration of [REDACTED] (3-7 Days Prior), and SPK-8016, and 30 (± 2) minutes, 2 hours (± 10 minutes), 5 hours (± 10 minutes), and 24 (± 1) hours from the completion of the SPK-8016 infusion. PAX Gene will be collected pre-administration of [REDACTED], pre-administration of SPK-8016, and 5 hours (± 10 minutes) and 24 (± 1) hours from the completion of the SPK-8016 infusion. Additional blood samples, including FVIII activity levels, will also be collected pre-infusion of SPK-8016.

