4.2 Study Duration, Enrollment and Number of Sites

4.2.1 Duration of Study Participation

The study will consist of the following periods

- Screening period (up to a maximum of 16 weeks)
- Study Intervention: Assignment into cohort with possible pre-infusion immunosuppressive medication or administration of oral immunosuppressive medication, and then study product infusion
- Follow-up observation period (52 [± 2] weeks post-infusion of SPK-8016)

The total duration of the study for an individual participant is up to 68 weeks (including up to a maximum of 16 weeks of screening).

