5.1 Inclusion Criteria

Participants must meet all the following criteria at screening and prior to dosing of SPK-8016 (Day 0) to be eligible for the study:

1. Be able to understand the purpose and risks of the study and provide signed and dated informed consent and authorization to use protected health information (PHI) in accordance with national and local privacy regulations
2. Be male and ≥ 18 years of age
3. Have hemophilia A with:
 - a) $< 1\%$ (< 1 IU/dL) endogenous FVIII activity levels as historically documented by a certified laboratory **or** screening data results; OR
 - b) $1-2\%$ ($1-2$ IU/dL) endogenous FVIII activity levels and > 10 bleeding events per year (in the last 52 weeks prior to screening); OR
 - c) $1-2\%$ ($1-2$ IU/dL) endogenous FVIII activity levels and on prophylaxis
4. Have had > 150 prior exposure days to any recombinant and/or plasma-derived FVIII protein products or cryoprecipitates based on historical data from medical records/history
5. Have no prior history of hypersensitivity or anaphylaxis associated with any FVIII or IV immunoglobulin administration
6. Have no measurable inhibitor against FVIII at screening (i.e., < 0.6 Bethesda Units); no confirmed history of clinically significant FVIII inhibitor **and** no clinical signs or symptoms of decreased response to FVIII administration (Note: Family history of inhibitors is not exclusionary, nor is remote documentation (greater than 5 years) of a single measurement of Bethesda titer of > 0.6 BU that is not accompanied by clinical evidence of failure to respond to infused FVIII concentrate)
7. Have acceptable laboratory values sampled at screening and reviewed prior to Day 0:
 - a) Hemoglobin ≥ 11 g/dL;
 - b) Platelets $\geq 100,000$ cells/ μ L;
 - c) AST, ALT, alkaline phosphatase $< \text{ULN}$;
 - d) Bilirubin $\leq 1.5 \times \text{ULN}$ (Bilirubin levels above the laboratory's normal range are acceptable in individuals with a documented history or laboratory evidence of Gilbert's Disease);
 - e) Creatinine ≤ 2.0 mg/dL;
 - f) Absolute neutrophil count (ANC) ≥ 2000 per mm^3 ;

- g) Fibrinogen antigen \geq 180 mg/dL for participants in Cohort 2
8. Agree to use reliable barrier contraception after the administration of SPK-8016 until notified by the Investigator or designee.

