7.9.3 Prohibited Therapy

The following concomitant medications are not permitted during the study:

- Acetylsalicylic acid (aspirin) or ibuprofen; however, other non-steroidal anti-inflammatory drugs are permitted.
- Routine prophylactic treatment with FVIII product after Day 14 post vector infusion unless clinically indicated and in discussion with the Investigator and/or Sponsor.
- Routine prophylactic treatment with emicizumab unless clinically indicated and in discussion with the Investigator and/or Sponsor
- Any other investigational therapies prior to screening as defined in the exclusion criteria or used during the study

Any medication or herbal supplement that may cause liver toxicity should be avoided. If a medication with known liver toxicity cannot be avoided, the Investigator should discuss it with the Sponsor.

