7.9.4 Concomitant Procedures

A concomitant procedure is any therapeutic intervention (e.g., surgery/biopsy, physical therapy, tooth extraction) or diagnostic assessment (e.g., blood gas measurement, bacterial cultures) performed between the time the participant is enrolled (at screening) and the last study visit (Week 52/EOS). The use of concomitant procedures must be recorded in the eCRF.

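### No last-dose day is set for non-factor prophylaxis, so ABR28 and AIR28 could include residual-drug time for a man who stopped such a drug close to Day 0

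*Protocol*

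**What the plan says.** **Stopping prophylaxis.** Protocol 2.3.1.5, a risk paragraph, foresees bleeding "when the participants halt their prophylactic (factor or non-factor replacement) treatment after vector administration". The operative rules are in 7.9.2 and 7.9.3. Section 7.9.2 asks men to suspend prophylaxis during the study and allows FVIII prophylaxis for the first 14 days if medically necessary. Section 7.9.3 then prohibits "Routine prophylactic treatment with FVIII product after Day 14 post vector infusion", with an exception for clinical need. It also prohibits "Routine prophylactic treatment with emicizumab unless clinically indicated and in discussion with the Investigator and/or Sponsor". The FVIII line carries a day; the emicizumab line does not.

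**Entry.** Inclusion criterion 3c admits men with 1-2% "endogenous FVIII activity levels and on prophylaxis", without naming a type of prophylaxis. Criterion 3a (below 1%) sets no condition on prophylaxis at all. Exclusion 7 has a 12-week gap, but for investigational drugs only. Section 4.2.1 gives a "Screening period (up to a maximum of 16 weeks" and no minimum.

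**Analysis.** SAP 2 analyses all infused men. SAP 3.2.1 and 3.2.2 compute ABR and AIR from Day 0 and from Day 28. Efficacy follow-up (SAP 3.8) ends at withdrawal, last contact or loss of transgene expression. Nothing moves its start.

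**The concern.** The Day 28 start gives a man's earlier prophylaxis time to clear. That works for factor concentrate, which has a half-life of hours and a dated cut-off. It need not work for a drug with a half-life of weeks and no dated cut-off. Days that are free of bleeds and FVIII infusions because of residual drug would enter the ABR28 and AIR28 denominators and read as an SPK-8016 effect. AIR counts FVIII infusions only, so the non-factor drug itself would never appear in it.

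The readable SAP body would not reveal this. A drug started before Day 0 is classed as prior even if it continued, and prior drugs are summarised by class and product name (SAP 3.9.4). Duration of use is listed only for immunosuppressants (SAP 3.4.1). With few men per dose level and listings by participant, one man's ABR28 carries weight. ABR and AIR are the only efficacy endpoints in SAP 1.2.1.

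**Working it through.** The study is descriptive, so the plan has no power or sample-size figure to reproduce. The check uses the SAP's own formula plus assumed half-lives.

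**1. Window.** For a man followed to Day 364, EFF FUP = 364 + 1 = 365 days (SAP 3.8). The ABR28 denominator is 365 - 28 = 337 days, so one bleed gives 365.25/337 = 1.1 per year.

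**2. Does Day 28 clear FVIII?** Protocol 2.3.2 gives half-lives of 10.8 to 19.7 hours. Day 14 to Day 28 is 14 x 24 = 336 hours, or 336/19.7 = 17.1 to 336/10.8 = 31.1 half-lives. At most 0.0007% remains, so it does.

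**3. Does Day 28 clear a long-acting drug?** The documents give no non-factor half-life, so T = 14, 28 and 35 days are assumptions. After a last dose on Day 0, the fraction left at Day 28 is 2^(-28/T) = 25%, 50% and 57%. For these half-lives it does not.

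**4. Share of the window affected.** Let L be the last-dose day, and assume complete cover until 5% or 10% of drug remains. Cover ends on day L + T x log2(1/threshold), where log2(20) = 4.322 and log2(10) = 3.322. Share = max(0, that day - 28)/337. For example, with L = 0, T = 28 and 5%: 28 x 4.322 = Day 121.0, and (121.0 - 28)/337 = 27.6%.

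| Last dose | 5%: T = 14 / 28 / 35 | 10%: T = 14 / 28 / 35 |
|---|---|---|
| Day 0 | 9.6% / 27.6% / 36.6% | 5.5% / 19.3% / 26.2% |
| Day -28 | 1.3% / 19.3% / 28.3% | 0% / 11.0% / 17.9% |
| Day -56 | 0% / 11.0% / 20.0% | 0% / 2.7% / 9.6% |
| Day -112 | 0% / 0% / 3.3% | 0% / 0% / 0% |

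For T = 3 or 7 days with a last dose on Day 0, the 5% shares are 0% and 0.7%. The Day 28 start is clean at 5% when the last dose is no later than 28 - 4.322T, about Day -33, -93 or -123 for T = 14, 28 or 35.

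**5. From share to bias.** If d days of the window are covered and the bleed rate under residual drug is RR times the drug-free rate, expected ABR28 is 1 - (1 - RR) x d/337 of the drug-free value. With T = 28 and L = 0 at 5%, d = 93. RR = 0.1 gives 1 - 0.9 x 93/337 = 0.75, and RR = 0.5 gives 0.86. The shares in step 4 are therefore ceilings. A man who would not have bled anyway has no bias.

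**6. Other windows.** Section 6.8.2 lets men stay past Week 52. With 84 extra days the window is 337 + 84 = 421 and the same 93 days are 22%. If expression is lost at EFF FUP = 180, the window is 152 and they are 61%.

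**7. FVIII activity.** At Day 273 (39 full weeks), with L = 0 and T = 35, 2^(-273/35) = 0.4% of drug remains. The Week 40-52 median is not affected.

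**The case against.** The strongest reply is that the protocol already deals with this. Section 7.9.3 bars routine emicizumab during the study, without the 14-day allowance given to FVIII. If the study begins when "the participant is enrolled (at screening" (7.9.4), dosing should stop before the vector. Section 2.3.1.5 is risk prose, not a dosing rule. In the sponsor's sister trial emicizumab appears as treatment after lost expression (4.1.3); here, complete loss of expression ends ABR and AIR follow-up. All of that stands, so a last dose after the vector should be exceptional. It does not fix the gap before Day 0: the ban names one drug, has an exception and sets no date, and screening can be short.

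The design also centres on FVIII users: "All participants will administer a prophylactic infusion of 50 IU/kg of their current FVIII concentrate the morning of Day 0", and Section 6.4.1 requires a PK profile on the current FVIII product. This too stands. It makes an affected man less likely without ruling one out.

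A reader might infer that every man entering on a long-acting non-factor drug will have too low an ABR28. The table contradicts that, with several zero cells. A reader might also infer that the trial's efficacy result is inflated. The documents do not support that either. Protocol 4.1.1.1 states "The Primary Endpoint for efficacy for this study is the FVIII activity at steady state"; bleeds and infusions are also primary efficacy endpoints in 3.3, but no hypothesis is tested. Change in AIR is not shown to favour SPK-8016, because the prior-52-week baseline could be covered too and would then hold few FVIII infusions.

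Finally, medication dates are in the eCRF, prior drugs are shown by participant, and the SAP's list of tables and listings and the Table 1 grid are not visible. The statement about what would be shown is limited to the readable SAP body.

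**Conclusion.** The point holds conditionally and is minor. The plan dates the end of FVIII prophylaxis, does not date the end of non-factor prophylaxis, and uses one fixed start for both. For a man whose last non-factor dose fell close to Day 0, raw ABR28 and AIR28 could be too low in expectation. At the 5% threshold the ceiling is about 10-37% of a 337-day window for a Day 0 last dose, 1-28% for Day -28 and 0-3% for Day -112.

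These ranges rest on assumed half-lives of 14 to 35 days, an assumed threshold and complete cover. The bias is nil for short half-lives, long gaps or a man who would not have bled. The documents fix no size and show no such man enrolled.

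**What to change.** Keep the planned Day 0 and Day 28 values. In SAP 3.2.1 and 3.2.2, flag any man whose last routine prophylaxis was non-factor and list his last-dose date. For him, add a supplementary ABR and AIR, with events and denominator, from the later of Day 28 and five half-lives after that dose, using the product's labelled half-life.

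The cost is one derived date, one flag and some SAP wording. Medication start and end dates are already collected (Protocol 7.9.1), and nothing changes if no man qualifies. The downside is a different window and shorter evaluable time for affected men. With half-lives of 14, 28 or 35 days and a Day 0 last dose, 365 - 70 = 295, 365 - 140 = 225 or 365 - 175 = 190 of 337 days remain. With a Day -112 last dose, 337, 337 or 302 remain.

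Add a last-dose day to Protocol 7.9.3 only if dosing continues. SAP 1 describes the product's development in the past tense, so that amendment may have no use.
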